Study Rationale	
People with serious mental illnesses (SMI) are overrepresented across the criminal justice system. While incarcerated in prison, people with mental illness (MI) face higher rates of violence and behavioral infractions than the general prison population and experience administrative segregation (isolation) with more frequency and intensity. A growing body of literature suggests that to improve outcomes for incarcerated people with MI, mental health treatments need to be expanded to include interventions that directly address risk factors related to criminal activity. Specifically, these interventions must target the risk factors most closely associated with criminal activity (e.g. criminogenic risk factors). There are criminogenic interventions, such as Thinking for a Change (T4C)¹, which have been shown to significantly reduce criminal offending, behavioral infractions and time in administrative segregation among general offenders. Despite promising evidence, criminogenic interventions are not used with prisoners with mental illness because of neurocognitive and social impairments associated with mental illness inhibits their use with this population. Thus, these interventions must be adapted in order to be used effectively with people with mental illness.

Study Objective(s)	
Primary
 
• To test the study intervention's ability to engage the study outcomes (aggression, behavioral infractions, administrative segregation). 
Secondary
 
• To test the study intervention's engagement with the study treatment targets (impulsivity, interpersonal problem solving, and criminal thinking).
Test Article(s) (If Applicable)	The research intervention is Thinking for Change for prisoners with mental illness (T4C-MI) ¹ . This intervention has two components. The first component is Thinking for a Change (T4C), a CBT based group intervention that includes three treatment modules delivered over the course of 25-sessions in a closed-group format to 8-12 people up to twice a week over 12-14 weeks. The second component of T4C-MI is the Targeted Service Delivery Approach (TSDA) that this research team developed for use during the delivery of T4C to compensate for the impact of the neurocognitive and social impairments associated with mental illness on participants' ability to fully engage in and understand T4C's intervention materials.
Study Design	This study will use an RCT to conduct a pilot effectiveness trial of the study intervention. Participants in this study will be randomly assigned to

one of two study arms: 1) the experimental condition which involves the study intervention T4C-MI and 2) the control condition which involves standard prison treatment and programming. The pilot study will take place in up to four facilities in the North Carolina Prison system.

Subject Population key criteria for Inclusion and Exclusion:	
Study inclusion criteria include:
 
(a) aged 18 years or older;(b) have a diagnosis of schizophrenia, schizoaffective disorder, psychotic disorder, bipolar disorder or major depressive disorder(c) have moderate to high criminogenic risk levels as determined by the Level of Service Inventory(d) have at least one year or more remaining on his or her prison sentence at the time of the screening interview. 
Study exclusion criteria include:
 
(a) an intellectual or developmental disability;(b) have assault precautions or other restrictions that would preclude the person from being in group gathering spaces within the prison where the intervention will take place; and(c) participation in T4C in the last 6 months.
Number Of Subjects	Up to 112
Study Duration	
• Each subject's participation will last 9 months• This study will be active for 4 years.
Study Phases	
(1) Study Recruitment and Informed Consent
 
A) Prison Staff will provide study personnel with list of potentially eligible participants.B) Study staff will invite potentially eligible participants to meet with them to discuss study. Study staff will complete informed consent with all potential participants who agree. 
(2) Study Screening- All potential participants who agree to participate in the study after informed consent is completed will participate in a screening interview to determine study eligibility.
 
(3) All participants who are found eligible at the end of the screening interviews will be randomized to one of the two study arms (e.g. experimental or control condition). These individuals will make up the study sample
 
(4) Baseline interviews will be completed with all study participants.
 
(5) Study participants who are randomized into the experimental condition will participate in the study intervention. Those who are randomized into the control condition will receive standard prison treatment and programming.
 
(6) Follow up: Study participants will participate in follow-up interviews at 3- and 6- months post-baseline.
 
(7) Administrative data related to behavioral infractions and administrative segregation will be gathered at 9-months post-baseline.

Screening	
Study Treatment	
Follow-Up	

The statistical analyses of this study will explore the treatment effect of the study intervention on the study outcomes (aggression, receipt of behavioral infractions, and time spent in administrative segregation) and the study treatment targets (impulsivity, social problem solving, and criminal attitudes and associates). Additionally, mediation analyses will be conducted to explore whether treatment effects on study outcomes operate indirectly through study treatment targets.

DATA AND SAFETY MONITORING PLAN	This is a small-scale, pilot study with a relatively small number of subjects; thus, in lieu of a Data and Safety Monitoring Board, the PI will perform the monitoring function as part of the general oversight and scientific leadership of the study
---------------------------------	---

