6. STUDY PROCEDURES

Study participants will complete up to four, face to face interviews. The first interview is the screening interview where study eligibility is determined. Participants who meet the study eligibility criteria are enrolled in the study, randomized into one of the two study conditions. People who are randomly assigned to the experimental condition receive the study intervention and those who are randomly assigned to the control condition receive standard prison treatment and programming. All participants who are randomized to either study condition complete three additional follow up interviews: the baseline interview as well as 3- and 6-month interviews. Additionally, administrative data related to behavioral infractions and administrative segregation are collected at the 9-month time point.

6.a Description of Research Procedures

The study procedures are listed below.

All research interviews will take place in private locations in the prison:

First: Recruitment of study subjects will begin the month prior to the initiation of each intervention cycle. Correctional staff at the facility where the intervention is being delivered, will provide the research team with a list of all of the prisoners in their facility who meet the following criteria: a) 18 years and older: b) have mental health issues: c) have at least 1 year remaining on his or her prison sentence: d) do not have any restriction that would preclude the person from being in group gathering spaces within the prison; and e) do not have an intellectual or developmental disability.

Second: Research staff will go to the prison and invite potentially-eligible prisoners to meet with them in a private setting to learn about the study. During this initial meeting, research staff will provide participants with a flyer that describes the study and discuss potential participant's questions. The study flyer and discussions with potential participants will include information about the voluntary nature of the study and will explain that the person's decision about participation has no bearing on the person's criminal or civil cases. The research staff will also explain that the participant can end his or her participation in the study at any time during the recruitment or study process without negative consequences.

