Three: Immediately after completing the recruitment meeting research staff will complete Informed consent with all participants who express interest in participation in the study. This meeting will take place in a private setting in the prison.

Fourth: Research staff will complete a screening interview immediately after the informed consent process with all potential subjects who agree to participate in the study after completing informed consent. The study screening interview will determine whether participants are eligible to participate in the study by screening for mental health diagnoses, criminogenic risk levels, and prior engagement in T4C.

Fifth: At the end of the screening interview potential participants will be informed whether they meet the study eligibility criteria. Participants who are found eligible for the study and agree to participate will be assigned to a study condition. During the RCT phase of the study, participants will be randomized into one of two conditions, the research intervention (T4C-MI) or the control condition (Standard prison treatment and programming). The research staff will randomly assign participants to a study condition by opening a sequentially numbered envelope and discussing the condition assignment with the participant. In order to be sure that interviews are not too long, the screening and baseline interviews will be broken into two separate interviews, conducted at least one day apart from each other. After randomization is complete the research staff will schedule a mutually agreed upon time to return to complete the baseline interview.

Six: Research staff will complete a baseline interview with all study participants. This interview will take place in a private location in the prison. The baseline interview will include a brief assessment of participant's neurocognitive functioning, clinical and criminal justice history, and baseline assessments of treatment targets and study outcomes. The baseline interview will take 60-90 minutes to complete.

Seven: Research staff will complete follow-up interviews with all study participants at 3-, 6 -months after the baseline interview. Each interview is expected to take 30-60 minutes to complete and will be conducted in a private setting in the prison. Participants' outcomes will also be assessed at 9 months post release using administrative data.

6.b Informed Consent

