9. STATISTICAL ANALYSIS

Given the preliminary nature of this study, statistical analyses of our outcomes will not be conclusive; rather we will examine the data for trends across time rather than relying exclusively on tests of statistical significance.

9.a. Primary Outcomes

The primary outcomes of this study are: Aggression, Receipt of Behavioral Infractions, and Time Spent in Administrative Segregation (see Appendix B).

9.b. Secondary Outcomes

The secondary outcomes of this study are those measures listed as Treatment Targets in the conceptual model: Interpersonal Problem Solving, Criminal Attitudes and Associates, and Levels of Impulsivity (see Appendix B).

9.c. Statistical Methods

Treatment Targets and Study Outcomes that are collected via a standardized measure (i.e. Social Problem Solving, Criminal Attitudes and Associates, Impulsivity, and Aggression) are collected at baseline as well as during follow-up periods (see Appendix A). Study Outcomes that are collected via administrative data (i.e. receipt of behavioral infractions and time spent in administrative segregation), however, are not collected as baseline, rather are summed cumulatively over the period extending from the 3-month follow-up period through the 9-month follow-up period.

To examine the impact of T4C-MI on study outcomes that are measured dichotomously and only collected during follow-up periods (i.e. receipt of disciplinary fractions and administrative segregation), we will use chi-square tests to examine between-group differences during the post-test period. To examine between-group post-test differences when these outcomes are measured as counts (i.e. number of behavioral infractions received and days spend in administrative segregation), nonparametric tests will be used to test differences in group medians (e.g. Mann-Whitney Test) and regressions that can accommodate count data (e.g. Poisson, negative binomial) will be employed.

For Treatment Targets and Study Outcomes that are measured continuously and collected at both baseline and follow-up periods (i.e. Social problem solving, impulsivity, criminal attitudes and associates, and aggression), we will use T-tests to examine between-group differences at posttest as well as mixed effects linear models where measurement occasion at level 1 is nested within the individual at level 2.

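### The infraction and segregation window is timed from a baseline interview held after randomisation, so a randomised person who misses that interview has no stated start or end date for two record-based primary outcomes

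*Combined protocol and SAP*

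**What the plan says.** All references are to the combined protocol and SAP.

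- **Sample.** Synopsis, Study Phases (3), says of the eligible people who are randomised: "These individuals will make up the study sample".
- **Order of events.** Under 6.a (Fifth), the envelope is opened at the end of screening and the assignment is discussed with the participant. Then: "After randomization is complete the research staff will schedule a mutually agreed upon time to return to complete the baseline interview". The only limit on the gap is a minimum; the screening and baseline interviews are "conducted at least one day apart from each other". Section 3.a says staff are not blinded.
- **Clock.** Study Phases (7): "Administrative data related to behavioral infractions and administrative segregation will be gathered at 9-months post-baseline". Section 6.a (Seven): "Research staff will complete follow-up interviews with all study participants at 3-, 6 -months after the baseline interview". The same item then dates the administrative outcomes nine months after release, which does not agree with Study Phases (7).
- **Counting window.** Section 9.c says the two record-based outcomes are "summed cumulatively over the period extending from the 3-month follow-up period through the 9-month follow-up period".
- **Source.** Section 6.c and Appendix A take both outcomes from administrative data, not interviews. Section 6.b places the records authorisation with informed consent, which 6.a puts before screening and randomisation.
- **Withdrawal.** Section 11.b withdraws from the intervention and the study anyone who declines further participation in the intervention or follow-up interviews, or who is transferred or released from the prison delivering the intervention. It is silent on records.

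**The concern.** Prison records need no cooperation from the participant after consent, so these two outcomes could be close to complete for everyone randomised. The plan ties their dates to an event that needs cooperation and access, and that happens once the arm is known. A person who is in segregation, declines, or is moved before the baseline interview has no day 0, and therefore no month 3 or month 9.

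Whether that interview takes place, and when, could differ by arm. It could also depend on segregation, which is itself a primary outcome. Analysts would then have to decide afterwards whether to leave such people out or invent a date for them. Section 9.d gives attrition, retention and inputs for a later power calculation as the main purpose of the pilot. Avoidable loss that may be related to the outcome would distort those inputs.

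**Working it through.** There is no stated figure to reproduce, so the check is of the order of events, the window arithmetic and the size of the gap. One month is taken as 365.25/12 = 30.44 days.

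**1. Is a window defined for everyone randomised?** The order is consent and authorisation, screening, randomisation and disclosure, then baseline interview. Months 3 and 6 run from that interview, and the records point is nine months post-baseline. Without a baseline interview neither end of the 9.c window can be computed. No section supplies a substitute date. The after-release anchor in 6.a does not help, because inclusion criterion (d) requires at least one year left on the sentence at screening.

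**2. Where the window falls, in days since randomisation.** For a gap of g days it runs from 91.3 + g to 273.9 + g.

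| Gap g (assumed, except the 1-day minimum) | Window | Shift as share of six months (g/182.6) |
|---|---|---|
| 1 day | 92 to 275 | 0.5% |
| 14 days | 105 to 288 | 7.7% |
| 30 days | 121 to 304 | 16.4% |
| 60 days | 151 to 334 | 32.9% |

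Dated from randomisation, the window would be about day 91 to day 274 for all of up to 112 people.

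**3. How many people could be affected.** The documents give no rate of missed baseline interviews. At assumed rates: 112 × 0.03 = 3.4; 112 × 0.05 = 5.6; 112 × 0.10 = 11.2. That is about 3, 6 or 11 people.

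**4. What differential loss could do (all rates assumed).** Let the true proportion with an event be 50% in both arms. One arm loses a fraction d, in whom the proportion is 70%. The observed proportion in that arm is (0.50 − 0.70d)/(1 − d).

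- d = 0.10: 0.43/0.90 = 47.8%, a spurious difference of 2.2 points.
- d = 0.20: 0.36/0.80 = 45.0%, a spurious difference of 5 points.

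**5. Late 3-month interview (conditional).** If the count opened on the actual interview date and closed at nominal month 9, a delay of 14 or 28 days would remove 14/183 = 7.7% or 28/183 = 15.3% of the window.

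**6. Overlap with delivery under a randomisation clock.** Delivery takes 12-14 weeks, or 84-98 days. Assume randomisation 30 days before the first session, so delivery ends on day 30 + 84 = 114 to 30 + 98 = 128.

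- Window opening on day 91 (randomisation clock): 114 − 91 = 23 to 128 − 91 = 37 delivery days fall inside it.
- Baseline clock, interview one day after randomisation (opens day 92): 22 to 36 days.
- Baseline clock, interview at the first session (opens day 121): 0 to 7 days.

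Both clocks can overlap with delivery. The randomisation clock overlaps more, by an amount that depends on the gap.

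**The case against.** The strongest reply is that the plan excludes nobody. Study Phases (4) intends a baseline interview for every participant, and Study Phases (7) says when records are gathered, not who is counted. A reader might infer that people without a baseline interview are dropped from the record-based outcomes. The documents do not say so, and that inference should not be made. What stands is narrower: an intention to interview everyone is not a rule for a missed interview, and no dates are given for that case.

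Second, long gaps are unlikely. Section 6.a says "Recruitment of study subjects will begin the month prior to the initiation of each intervention cycle", and Appendix A places the baseline interview before delivery. Both points are fair, but neither sets a latest date, and a short gap does not help someone who is never interviewed.

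Third, 11.b governs much of the loss. The opening of section 6 counts baseline among the follow-up interviews, so someone who declines it, or is transferred first, may be withdrawn whatever the clock. This stands: re-dating the window does not by itself recover these people, and 11.b has to change too. Segregation before baseline is the route that rests mainly on the clock.

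Fourth, a reader might infer that segregation days are lost whenever the 3-month interview runs late. Section 9.c refers to a follow-up period, not an interview date. Days before a late interview drop out only if the actual interview date is used, and the window shortens only if its end also stays at nominal month 9. The plan does not state that mixed rule. This is an ambiguity to close, not a demonstrated loss.

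Finally, section 9 says the analyses will not be conclusive. That limits how much the gap matters, but retention data are a stated purpose, so a clear rule is still useful.

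**Conclusion.** The point holds as a gap in definition, and closing it is a cheap improvement. Two of the three primary outcomes have no stated window for a randomised person who misses the baseline interview, although records exist and the sample is everyone randomised. The withdrawal rule leaves records collection unresolved, and the two anchors for the nine-month records point conflict.

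The size is not known from the documents. About 3 to 11 of 112 people follows from an assumed 3% to 10%. The biases of 2.2 and 5 points rest on assumed event rates and on loss confined to one arm; they show a mechanism and are not forecasts. The text does not support a claim that these people are excluded, or that late 3-month interviews will remove segregation days.

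**What to change.** 1. In Study Phases (7), 6.a, 9.c and Appendix A, define the window for infractions and segregation by fixed calendar days from an origin that does not depend on whether or when any interview took place. The randomisation date is simplest. Apply it to everyone randomised. Interviews can stay scheduled from the baseline interview.
2. In 11.b, state that withdrawal from the intervention or interviews does not stop records collection where the signed authorisation still stands.
3. In 6.a (Seven), reconcile the after-release wording with Study Phases (7).

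**Cost.** Protocol and SAP wording only; the data source is unchanged. There are two downsides. Record and interview time points no longer share day 0. A randomisation-dated window also opens somewhat earlier relative to delivery, so the fixed opening day should be chosen with the intended post-test period in mind, not set at day 91 by default.

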1. BACKGROUND AND RATIONALE

1.a. Background

People with serious mental illnesses (SMI) are overrepresented across the criminal justice system. While incarcerated in prison, people with mental illness (MI) face higher rates of violence and behavioral infractions than the general prison population and experience administrative segregation (isolation) with more frequency and intensity. These experiences substantially increase negative outcomes for prisoners with MI, including exacerbated symptoms of mental illness and trauma. Moreover, following release, more than 60% of people with MI return to custody within three years, creating an incarceration–punishment cycle at great personal and social cost. This cycle clearly underscores an urgent need for interventions designed to reduce levels of aggression, behavioral infractions, and time in isolation among prisoners with MI, with the overall aim of improving outcomes among this population both while incarcerated and after release.

1.b. Study Rationale

Extant research posits that the best predictors and risk factors for criminal activity are the same for people with SMI and those without SMI^{2,3}. These factors, called criminogenic risks, are derived from the Risk Needs Responsivity model (RNR) and include anti-social behavior, anti-social personality, anti-social cognitions, anti-social associates, substance use, family conflict, school or work problems, and lack of pro-social leisure activities^{4–6}. There is evidence that, compared to non-SMI justice-involved persons, justice-involved persons with SMI have higher overall levels of criminogenic risk factors^{7,8} and higher levels of specific criminogenic risk factors such as criminal thinking and criminal attitudes^{9–12}. The growth in our understanding of the nature and extent of criminogenic risk factors among justice-involved persons with SMI has led some experts to suggest that in order to achieve optimal mental health and criminal justice outcomes in this population, mental health services need to include interventions that directly address criminogenic risk factors^{13,14}.

A number of community-based mental health interventions have been developed to divert people with SMI away from jails and prisons. These interventions include pre- and post-booking jail diversion services^{15,16}, community reentry services^{17,18}, mental health courts^{19,20}, and specialized probation caseloads²¹. These interventions have had some success at reducing mental health symptoms, but none have been able to improve criminal justice outcomes for people with SMI^{22–25}. Moreover, virtually none of this research has focused on improving the outcomes of persons with mental illness while incarcerated in prison, and this is a remarkable gap in our understanding given the increased risk of behavioral infractions

and administrative segregation for prisoners with SMI. In order to break the cycle of behavioral infractions, administrative segregation and further deterioration in mental health functioning, which characterizes the experiences of the large and growing population of people with SMI in prisons, prison-based mental health interventions must directly target the criminogenic risk factors most strongly associated with criminal activities. For the general offender population, a group of cognitive behavioral interventions, known as criminogenic interventions, have been shown to be effective at addressing criminogenic risk factors. However, the neurocognitive and social impairments associated with SMI impede their use with this population, which creates a critical gap in services for justice involved people with serious mental illnesses generally and those that are incarcerated specifically.

